Exclusion criteria: Patients with previous prescription of opioid medication or non-opioid medication between 01.01.2012 and index treatment will be excluded. Patients with cancer treatment, palliative care or opioid substitution after index treatment will be excluded.

Follow-up: Patients' follow-up period include 5 years after start of opioid resp. non-opioid treatment and chronic pain diagnosis between 01.01.2013 and 31.12.2017. Each patient will be censored at death (death date), switching of study group (opioid --> non-opioid or vice versa), 12 months without treatment or followed-up 5 years until last known record for the patient in the German health claims database, latest at 31.12. 2017 (end of latest data cut), whichever happens first.

Variables:

Outcome Variables include death by any course as primary endpoint and hospitalization due to any course, hospitalization with misuse, addiction diagnoses, outpatient diagnosis of misuse or addiction and treatment procedures as secondary endpoints.

Exposure Variables are pain treatments including opioid and non-opioid treatments.

Other Covariates will be collected for assessments over the course of the study: Age and gender (sex: male, female), charlson comorbidity index. Comorbidities, comedications, region will be collected for Propensity Score Matching.

Data Analysis: The main analysis will focus on each of the 2 main cohorts with chronic pain patients as defined at inclusion and:

- with opioid treatment between 01.01.2013 and 31.12.2017 (named cohort A)
- with non-opioid treatment between 01.01.2013 and 31.12.2017 (named cohort B)

To address the group comparisons adequately, a propensity score matching will be conducted. The main analyses will include a multivariate Cox proportional hazards regression. Additional stratified analyzes will be carried out as follows: Subgroup analyses for each following pain conditions will be conducted: headache (R 51*); pain, not elsewhere classified (R52*); persistent somatoform pain disorder (F45.4*); polyneuropathy in diabetes (E10.4*-E14.4 plus G63.3), kyphosis and lordosis (M40), scoliosis (M41), spinal osteochondrosis (M42), other deforming dorsopathies (M43), ankylosing spondylitis (M45), other inflammatory spondylopathies (M46), spondylosis (M47), other spondylopathies (M48), and spondylopathies in diseases classified

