9.1 Study Design

This is a retrospective observational cohort study based on an anonymized German health claims database. This database contains data on around 4 million insured people from 69 German statutory health insurances (SHI). This research database is a complete, longitudinal claims dataset of approx. 7 million individual patients (ca. 10% of the statutory insured population of Germany) between 2012 and 2017. The analyses for this study will be done on a 4 million patients subset that is stratified by age

and gender based on the 2013 population structure of Germany as reported by the German Federal Statistical Office DeStatis.

This study consists of two cohorts: opioid and non-opioid patients. Only patients who started their therapy between 2013 and 2017 and had no therapy in 2012 (therapy naïve patients) will be included in the study.

Exposure time is defined as max. 5 years after the initial prescription for each patient, so that exposure time is max. 60 months per patient.

Exposure time may end before the end of study if patient died, stopped treatment (end of follow-up after 1 year without treatment with opioids / other pain medication), changed treatment group (from opioids to other pain medication or vice versa) or was lost to follow up due to other reasons (e.g. change of insurance), whichever occurs first.

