9.2.1 Study Period

Due to data protection regulations in Germany, only an extract of maximum 6 years of data coverage could be available for the research purposes: 1st January 2012 to 31st December 2017.

The **baseline period** is defined as the period prior to the date of first diagnosis of diagnoses or first opioid or non-opioid treatment initiation as described in inclusion criteria (Chapter 9.2.2.1). The baseline assessment period endures between January 01, 2012 and first study medication prescription.

Index treatment is defined as the date of first opioid or non-opioid treatment prescription between 1st January 2013 and 31st December 2017.

Exposure time is defined as time between index treatment and December 31, 2017. Considering data availability of a maximum of 6 years and prescription in a required time period of 60 months, exposure time endures maximum five years. Thus, patients can be censored at death (death date in the linked records), last known record for the patient in the German health claims database, switching of treatment groups (from opioid group to non-opioid group or vice versa), 12 months without opioid/non-opioid treatment or 31st December 2017 (end of latest data cut), whichever comes first.

[figure not shown]
The **outcomes** will be assessed between index treatment and 31.12.2017.

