9.4.2 Outcome Assessment

The study will assess the following main outcomes during the follow-up period.

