9.4.2.1 Primary endpoint

Primary endpoint is **death** by any course in the study follow-up. Death will be assessed during the follow-up period by number of patients who deceased during follow-up period (2013 – 2017) via the date of death in German claims data base. Additionally, mortality rate will be estimated as number of patients who died during the follow-up divided by person-time

of follow-up, censoring at time of death, last known record for the patient in the database, or 31st December 2017 (end of latest data cut), whichever is earlier.

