9.4.2.2 Secondary endpoints

Secondary endpoints are following:

- **Hospitalization due to any course.** Hospitalization will be assessed via the number of hospitalisations (calculated by counting the number of discharge dates (KH_Fall. Entlassungsdatum) in the year of interest, hospitalization rate, and length of stay in the hospital (KH_Fall. Verweildauer). The rate of hospitalization will be estimated as the number of patients with at least one hospitalization during the follow-up period divided by person-time of follow-up, censoring at time of death, last known record for the patient in the database, or 31st December 2017 (end of latest data cut), whichever is earlier.
- **Intensive care unit (ICU-stay)** stay is defined as patient's stay based on specialty of department in hospital (KH_OPS.Fachabteilung = 3600).
- **Hospitalization with to misuse or addiction.** The hospitalization with misuse or addiction will be analysed, if principal (main) diagnosis at discharge date between January 1st 2013 and December 31st 2017 contains at least one ICD-10 diagnosis of misuse/addiction: F10* or F11* or F13* or F19* or T40* (see also Appendix B in **Fehler! Verweisquelle konnte nicht gefunden werden.**).
- **Hospital admission diagnoses.** We report the hospital admission diagnoses based on ICD-10 codes between January 1st 2013 and December 31st 2017.
- **Coding of procedures in hospitals** that indicate number of patients that were hospitalized with severe diseases such as cardiovascular

diseases will be assessed via OPS-Codes provided in Appendix B as an excelsheet.

- **Coding of a misuse or addiction diagnosis in the outpatient sector** will be assessed via number of codings of misuse/addiction (ICD Codes = F10* or F11* or F13* or F19* or T40*) in outpatient sector by general practitioner or a specialist (e.g. psychiatrist), as ensured diagnosis (Diagnosesicherheit='G'). Additionally, the number of patients with a least one coding of ICD 10 codes of an ensured misuse/addiction in outpatient sector by general practitioner or a specialist (e.g. psychiatrist) will be assessed.
- **Sick leave** will be assessed as an absolute number and relative frequencies of patients with an attest of inability to work (patients with attest of inability to work as a percentage of all patients) in 2013-2017 and number of days being off work.
- **Hospital deaths** will be assessed via reason of discharge = death (Entlassgrund = Tod)

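### The hospitalization rate counts each patient once but lets person-time run past the first admission; the censoring lists for the rates conflict with the general follow-up rule; and, depending on that rule, Chi² and t-tests on secondary counts may compare follow-up length rather than risk

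*Protocol*

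**What the plan says.** Section 9.4.2.2 gives three hospitalization measures: a number, "calculated by counting the number of discharge dates" in the year of interest; length of stay; and a rate, "estimated as the number of patients with at least one hospitalization during the follow-up period divided by person-time of follow-up".

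For both the mortality rate (9.4.2.1) and the hospitalization rate (9.4.2.2), person-time ends at the earliest of three events: "censoring at time of death, last known record for the patient in the database, or 31st December 2017 (end of latest data cut").

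The general rule is longer. The protocol summary, under Follow-up, says: "Each patient will be censored at death (death date), switching of study group", and adds 12 months without treatment. Section 9.1 has "Exposure time may end before the end of study if patient died, stopped treatment", explains in brackets that follow-up ends after a year without treatment, and adds change of treatment group. Section 9.2.1 lists "switching of treatment groups (from opioid group to non-opioid group or vice versa), 12 months without opioid/non-opioid treatment" among the censoring events, but then says that outcomes "will be assessed between index treatment and 31.12.2017". Section 9.4.2 says: "The study will assess the following main outcomes during the follow-up period".

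Section 8.2 asks whether the number of hospitalizations, length of stay, and number of outpatient misuse and addiction diagnoses differ between the cohorts. Section 9.7.1 assigns questions about differences between the treatments to Chi² and t-tests at the 5% level. It also names Cox regression for the main research questions, without linking it to these secondary counts.

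**The concern.** Three linked matters are at stake.

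1. The rate formula suits death, because death ends person-time. Hospitalization does not. A patient admitted in month 2 and observed for five years adds one event and the full five years.
2. Two analysts who both follow the protocol could count different deaths over different person-time. One stops at a switch or a 12-month gap; the other runs to the data cut. The mortality rates and the Cox hazard ratio could then describe different follow-up.
3. Chi² and t-tests take no account of time at risk. Misuse codings and hospitalizations accumulate with follow-up, as does length of stay if summed. If one cohort leaves follow-up sooner, it shows fewer events at the same underlying risk.

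**Working it through.** The protocol gives no hospitalization rate, exit rate or cohort size, so there is no figure of its own to reproduce. Unless marked otherwise, the values below are assumptions.

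**(1) Hospitalization rate.** With constant first-event hazard h and follow-up T, the defined rate is (1 − exp(−hT))/T. Stopping person-time at the first event would return h. As a share of h, the defined rate is:

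| h per year | T = 1 y | T = 3 y | T = 5 y |
|---|---|---|---|
| 0.1 | 95% | 86% | 79% |
| 0.2 | 91% | 75% | 63% |
| 0.5 | 79% | 52% | 37% |

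*Similar follow-up.* Take T uniform from 0.75 to 5 years, the shortest and longest treatment durations in section 9.4.1. Mean T is 2.875 years. The mean of 1 − exp(−hT) is 1 − [exp(−0.75h) − exp(−5h)]/(4.25h).
- h = 0.30: 0.5487/2.875 = 0.191 per year.
- h = 0.20: 0.4202/2.875 = 0.146 per year.
- The ratio is 1.31 instead of 1.50. For 0.15 against 0.10 it is 1.39; for 0.45 against 0.30 it is 1.24.

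*Unequal follow-up.*
- Equal hazards of 0.20, 1.5 against 2.5 years: 0.1728/0.1574 = 1.10 instead of 1.00.
- 0.30 over 1.5 years against 0.20 over 4 years: 0.2416/0.1377 = 1.75 instead of 1.50.
- 0.30 over 4 years against 0.20 over 1.5 years: 0.1747/0.1728 = 1.01 instead of 1.50.

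The distortion can go either way.

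**(2) End of follow-up.**

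| Section | Switch of group ends it? | 12 months without treatment ends it? |
|---|---|---|
| Summary (Follow-up), 9.1, 9.2.1 censoring list | yes | yes |
| 9.4.2.1 and 9.4.2.2 rates | not listed | not listed |
| 9.2.1 outcome window | not listed | not listed |

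Section 9.3.2, on the Cox model, states no censoring rule of its own.

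To illustrate the 12-month gap, the hazards use the range of 100 to 200 deaths per 10,000 person-years in section 9.3.1. Assume 0.02 per year on opioids, falling at once to 0.01 on stopping, and 0.01 in the comparator. Time to data cut is uniform over 0.75 to 5 years, and stopping occurs at rate d after 0.75 years. The rate ratio is then (0.02 × time before stopping + 0.01 × time after stopping)/(total time × 0.01), which equals 1 plus the share of person-time before stopping.

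| d per year | Ends after 12-month gap | Runs to data cut |
|---|---|---|
| 0.15 | 1.92 | 1.87 |
| 0.30 | 1.86 | 1.77 |
| 0.60 | 1.78 | 1.64 |

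If mortality does not change on stopping, the two windows agree.

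**(3) Tests without person-time.** Assume the same misuse-code hazard, 0.02 per year, in both cohorts and n = 5,000 per cohort. Chi² = n(p₁ − p₂)²/[2p̄(1 − p̄)], with a 5% critical value of 3.84. Rows 3 to 5 use the same entry distribution in both cohorts, exit after 0.75 years, and mortality of 0.01 per year. Row 6 differs only in mortality.

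| Scenario | Mean follow-up, years | Chi² |
|---|---|---|
| Fixed follow-up, 4.88% vs 5.82% | 2.5 vs 3 | 4.4 |
| Fixed follow-up, 5.35% vs 5.82% | 2.75 vs 3 | 1.1 |
| Switching 0.6 vs 0.2 per year, 3.5% vs 4.6% | 1.79 vs 2.35 | 7.2 |
| Switching 0.4 vs 0.2 per year | 2.02 vs 2.35 | 2.3 |
| Stopping 0.6 vs 0.2 per year, 12-month rule | 2.32 vs 2.60 | 1.6 |
| Run to data cut, mortality 0.02 vs 0.01 per year | 2.78 vs 2.83 | 0.04 |

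Hospitalization counts summed over follow-up behave the same way. At an equal 0.20 per year, the third row gives means of 0.20 × 1.79 = 0.36 and 0.20 × 2.35 = 0.47. Chi² grows in proportion to cohort size.

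**The case against.** On (1), the rate is one of three hospitalization measures, it is secondary, and no rate ratio is planned. It is also a clearly specified, computable quantity. This limits the weight of the point. The formula is nevertheless fixed in the protocol, so a later analysis plan following it would inherit the fault.

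On (2), the three-item lists could be shorthand, since they refer to person-time of follow-up and other sections say when follow-up ends. The 9.2.1 outcome window could likewise be only the outer calendar limit. Both readings are possible, but the rate definitions do not refer back to the general rule, and the ambiguity reaches the mortality rate of the primary endpoint. Treating switching and stopping as ends of exposure only does not resolve it, because the summary and section 9.1 apply them to follow-up.

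On (3), much of the objection stands. Section 9.7.1 does not tie a test to each endpoint, and the hospitalization number is counted by year, which limits accumulation. Year of index treatment is in the propensity score (9.3.1), so staggered entry alone should be roughly balanced after matching. Four of the six illustrated values lie below 3.84. The concern is therefore conditional on unequal exit and on how (2) is settled.

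A reader might extend (3) to sick leave. Section 8.2 asks only how many sick-leave days each cohort has and poses no comparison, so the document does not support that.

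**Conclusion.** Part (1) is wrong as written: the rate understates the first-event rate, by 5% to 63% across the table above, and depends on follow-up length. A reader might infer that it always pulls a comparison toward no difference. That holds when follow-up is similar, but not in general.

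Part (2) is a conflict that needs reconciling. The mortality rate and the Cox model may rest on different deaths and person-time; the text does not establish that they do.

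Part (3) is a conditional risk for the number of hospitalizations, length of stay, and misuse and addiction diagnoses. Significant differences at equal risk arise in some assumed scenarios and not in others.

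The sizes of (2) and (3) cannot be determined from the protocol. A reader might also conclude that the primary mortality result is compromised. Parts (1) and (3) do not touch the primary Cox comparison, and (2) leaves its follow-up rule in need of clarification without showing bias.

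**What to change.** 1. In 9.4.2.2, report first hospitalizations over person-time to first hospitalization or end of follow-up, or all hospitalizations over total person-time. The second option needs the yearly discharge-date counts summed over the same follow-up as the denominator.
2. Reconcile the summary, 9.1, 9.2.1, 9.4.2.1 and 9.4.2.2. State one primary end-of-follow-up rule that governs numerator, denominator and Cox model, and label any other window as a sensitivity analysis. Which rule is primary is for the study team to decide and justify.
3. In 9.7.1, compare hospitalization and misuse counts with rate models that use person-time, such as negative binomial with log person-time as offset, or with time-to-first-event models. State whether length of stay is per stay or summed; if summed, relate it to person-time. Report follow-up time and reasons for exit by cohort.

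The cost is wording in 9.2.1, 9.4.2 and 9.7.1, alignment of the summary and 9.1, and modest programming. Section 9.2 shows that admission, discharge, death, prescription and insurance dates are already in the database, so no new data are needed.

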8.2 Secondary objectives

In addition, present study aims to determine the risk of addiction/ abuse and hospital admissions among opioid users with chronic non-cancer pain compared to patients with non-opioid pain medication.

The secondary objectives will be addressed with following hypotheses:

- How often do patients on long-term opioid therapy and patients with non-opioid pain medication being hospitalized and how long do they stay in hospital?
- Does the number of hospitalizations and length of stay in hospital differ between patients on long-term opioid therapy compared to patients with non-opioid pain medication in time period of five years?
- How many misuse and addiction diagnoses were coded in outpatient sector for patients on long-term opioid therapy and patients with non-opioid pain medication in time period of five years?
- Does the number of outpatient misuse and addiction diagnoses differ between patients on long-term opioid therapy compared to patients with non-opioid pain medication in time period of five years?
- How many sick leave days do patients on long-term opioid therapy and patients with non-opioid pain medication have in time period of five years?

9. Research Methods

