9.2.2 Patient Eligibility

9.2.2.1 Inclusion Criteria

For the purposes of this study, the requested extraction of the database consists of population of patients with chronic non-cancer pain corresponding to the following criteria. Inclusion and exclusion criteria are also provided in Figure 2.

Figure 2: Inclusion and exclusion criteria

Cohort A

- Patients are included in the long-term opioid group if they started an opioid-therapy between 2013 and 2017 and received consecutive prescriptions for opioid medications over a minimum of 3 quarters, over a 60-month period between January 1, 2013, and December 31, 2017. The treatment will be assessed using the ATC codes of opioid treatment N02AA01, N02AA05, N02AB03, N02AE01, N02AX02, N02AX01, N02AX06 (see also Table 9-1) reported in reimbursed medicines to patients.

- Patients are only included if they have been diagnosed in at least three quarters in the study period with one of the following diagnoses: R51, R52*, M00*-M99*, G43*-G44*, G50.0 or G50.1, F45.4*, G62*, or E10.4*-E14.4 plus G63.3. At least one diagnoses must be between 1 January 2012 and index treatment and main and secondary hospital diagnoses (*i.e. Haupt- und Nebendiagnosen*) will be used to include the patients.

Cohort B

- Patients with non-opioid pain medication are included, if they received a medication therapy with anticonvulsants (gabapentin, pregabalin, carbamazepine), antidepressants or non-opioid analgesics (NSAIDs, Metamizole) over a minimum of 3 quarters, over a 60-month period between January 1, 2013, and December 31, 2017. The non-opioid treatment will be assessed using the ATC codes (N03AX12, N03AX16, N03AF01, see also Table 9-1) of treatment reported in reimbursed medicines to patients.
- Patients are only included if they have been diagnosed in at least three quarters in 2012 with one of the following diagnoses: R51, R52*, M00*-M99*, G43*-G44*, G50.0 or G50.1, F45.4*, G62*, or E10.4*-E14.4 plus G63.3. At least one diagnoses must be between 1 January 2012 and index treatment and main and secondary hospital diagnoses (*i.e. Haupt- und Nebendiagnosen*) will be used to include the patients.

All diagnoses that lead to patient inclusion when coded between 01.01.2012 and index treatment and in at least three quarters within the study period are provided in Table 9-2 below.

Table 9-1: List of ATC codes of study opioid and non-opioids

Name	ATC Code
Study opioids	
Morphine	N02AA01
Oxycodone	N02AA05
Fentanyl	N02AB03

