9.7.1 Planned Analyses

To address the main research questions, descriptive analyses, Cox proportional hazards regression and test for examining group differences (T-test and Chi² test) will be provided.

Descriptive analyses using mean, median, standard deviation, absolute and relative frequency, minimum and maximum will be reported.

To address the research questions about the differences between opioid and non-opioid treatment, inductive analyses using Chi² Tests and t-test with critical value at the 5% significance level will be employed.

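### The misuse/addiction endpoints count poisoning for the opioid drug class only, which biases the cohort comparison of addiction/abuse towards an opioid excess of unknown size

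*Protocol*

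**What the plan says.** Protocol section 8.2 sets a comparative and broadly worded aim, with the non-opioid cohort as comparator: "present study aims to determine the risk of addiction/ abuse and hospital admissions among opioid users with chronic non-cancer pain compared to patients with non-opioid" (sentence cut here). One of its listed questions is: "Does the number of outpatient misuse and addiction diagnoses differ between patients on long-term opioid therapy compared to patients with non-opioid pain medication".

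Section 9.4.2.2 turns this into two endpoints with one closed code list. A hospital stay counts if the main discharge diagnosis "contains at least one ICD-10 diagnosis of misuse/addiction: F10* or F11* or F13* or F19* or T40". The outpatient endpoint counts confirmed diagnoses from the same groups: "ICD Codes = F10* or F11* or F13* or F19* or T40*) in outpatient sector".

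Section 9.2.2.1 defines Cohort B by "anticonvulsants (gabapentin, pregabalin, carbamazepine), antidepressants or non-opioid analgesics (NSAIDs, Metamizole". Table 9-1 lists the corresponding ATC codes. Section 9.7.1 tests differences between opioid and non-opioid treatment with "Chi² Tests and t-test with critical value at the 5% significance level".

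**The concern.** A comparison of misuse between two drug groups needs an outcome that can register misuse of either group's drugs. This list combines two kinds of event. F10, F11, F13 and F19 are substance-use disorders. T40 is a poisoning code, and it covers the drug class that defines Cohort A. An overdose on a Cohort A drug is therefore an endpoint event. An overdose on a Cohort B antidepressant, NSAID or anticonvulsant is not, and neither is harmful use of an analgesic or antidepressant that does not cause dependence.

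Part of any observed excess in the opioid cohort could then come from what the list can see rather than from what happened to the patients. The wording at risk is a general statement about addiction or abuse on opioids relative to non-opioid pain medication.

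**Working it through.** **Step 1: code list against drug list.** The code meanings are those of the standard ICD-10 classification; the protocol does not spell them out.

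| | Use-disorder or harmful-use code in the list | Poisoning code in the list |
|---|---|---|
| Cohort A: opioids | F11 | T40 |
| Cohort B: NSAIDs, metamizole | none (F55 absent) | none (T39 absent) |
| Cohort B: antidepressants | none (F55 absent) | none (T43 absent) |
| Cohort B: gabapentin, pregabalin, carbamazepine | F19 may catch some | none (T42 absent) |
| Neutral between cohorts | F10, F13 | – |

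**Step 2: does anything else in the protocol correct this?** Matching (9.3.1) balances baseline covariates, not outcome capture. The only sensitivity analysis (9.8.2) concerns cancer. The limitations in 9.10 do not mention the imbalance. Section 9.10.1.2 argues that a large sample makes classification errors unlikely to matter. That does not hold for errors that differ between cohorts, as Step 5 shows. The inpatient bullet also points to Appendix B, which is not shown. The protocol describes that appendix elsewhere as the OPS procedure list, and the ICD list stands in full in both bullets.

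**Step 3: direction.** Per 1,000 person-years, let b be the background rate (alcohol, sedatives, other) in both cohorts and a the F11 and T40 events in Cohort A. Let cA and cB be the events on the missing codes in each cohort.

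- Ratio with the list as written: (b + a) / b
- Ratio with a symmetric list: (b + a + cA) / (b + cB)

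The written list gives the larger ratio when cA / cB < (b + a) / b. Every Cohort B patient takes the uncoded drugs by definition. Cohort A takes some of them as comedication (9.3.1 lists NSAIDs and metamizole), so cA is not zero, but it is plausibly below that limit.

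**Step 4: size, with assumed rates.** The protocol gives no misuse rates, so there is no figure to reproduce. Taking cB = 1:

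| b | a | Written list | Symmetric, cA = 0 | Symmetric, cA = 0.5 | Symmetric, cA = 1 |
|---|---|---|---|---|---|
| 5 | 3 | 8/5 = 1.60 | 8/6 = 1.33 | 8.5/6 = 1.42 | 9/6 = 1.50 |
| 5 | 1 | 6/5 = 1.20 | 6/6 = 1.00 | 6.5/6 = 1.08 | 7/6 = 1.17 |

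Both ratios keep all of Cohort A's F11 events, so a real dependence excess stays in each of them.

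The same point can be put as shares. Suppose true risk on the full construct is equal, and let sA and sB be the shares of events outside the list. The observed ratio is (1 − sA) / (1 − sB).

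| sB | sA = 0 | sA = 5% |
|---|---|---|
| 10% | 1/0.90 = 1.11 | 0.95/0.90 = 1.06 |
| 30% | 1/0.70 = 1.43 | 0.95/0.70 = 1.36 |
| 50% | 1/0.50 = 2.00 | 0.95/0.50 = 1.90 |

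**Step 5: chance of a spurious significant opioid excess.** Assumptions: two-sided 5% test (the protocol does not state sidedness), equal true five-year risk of 1%, sA = 0, and matched cohorts of n each. Without bias this chance is 2.5%.

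| n per cohort | sB = 10% | sB = 30% | sB = 50% |
|---|---|---|---|
| 3,000 | 6% | 24% | 61% |
| 10,000 | 11% | 64% | 98% |

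Example for n = 10,000 and sB = 30%: the difference is 0.010 − 0.007 = 0.003, and the standard error is √((0.010·0.990 + 0.007·0.993)/10,000) = 0.0013. The z value is about 2.31, and P(Z > 1.96 − 2.31) is about 64%. A larger sample makes the artefact more likely to reach significance.

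**The case against.** The construct is addiction and abuse, and most Cohort B drugs do not produce dependence. Leaving them out of an addiction endpoint can be a deliberate choice of scope, and more F11 codes among opioid users is the effect the study sets out to measure. F10 and F13 are neutral, and F19 can pick up some gabapentinoid misuse. All of this stands, and it confines the point to T40 and the missing harmful-use code. It does not explain why a poisoning code is present for one drug class only, when the stated aim is not limited to dependence.

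Adding the missing codes also carries a risk. Cohort B is partly defined by antidepressants, and poisoning codes include suicidal and accidental events. Merging them into one endpoint could create a bias in the other direction. This too stands, and it is why poisoning should be shown separately. T40 already has the same weakness.

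A reader might infer that nothing planned could reveal the imbalance. The protocol does not support that: section 9.4.2.2 also plans a listing of hospital admission diagnoses, which could show non-opioid poisonings descriptively. The listing covers hospital admissions only and does not enter the misuse comparison.

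**Conclusion.** The point holds in a limited form. One-sided poisoning and harmful-use coding biases the cohort comparison of addiction/abuse towards an excess in the opioid cohort. The direction rests on a larger share of events falling outside the list in Cohort B than in Cohort A. That is plausible from the drug definitions but not shown by data in the protocol. The size cannot be derived: every rate, share and cohort size in the illustration is assumed. If few Cohort B events are missed, the distortion is small (a ratio of 1.06 to 1.11 with 10% missed).

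Two stronger readings are tempting. One is that any opioid excess on these endpoints would be a product of the code list. That is not supported, because an F11 excess is a genuine drug effect. The other is that Cohort B cannot score at all. That is not supported either, because F10, F13 and F19 apply to both cohorts.

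Only the two misuse/addiction secondary endpoints are affected. All-cause death and all-cause hospitalization are untouched. Severity is minor to moderate.

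**What to change.** In both misuse/addiction bullets of section 9.4.2.2:

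1. Report the disorder codes (F10, F11, F13, F19) and the T40 poisonings as separate components.
2. Add a comparison on a symmetric list, applied to both cohorts. It should also include harmful use of non-dependence-producing substances and poisoning by non-opioid analgesics, antiepileptics and antidepressants. The candidate codes are F55, T39, T42 and T43, to be confirmed by the coding lead. Show poisoning separately from disorders, with a note that it includes suicidal and accidental events.
3. State that any general conclusion on addiction/abuse rests on the symmetric comparison. If the list stays as it is, rename the endpoint and limit the conclusion to opioid, alcohol, sedative and other-substance disorders, with T40 poisonings reported apart.

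The cost is a longer code list and a few extra table rows. The inpatient and outpatient ICD-10-GM diagnoses are already among the data described in section 9.2.
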